For more than two decades, selective laser trabeculoplasty (SLT) has been used safely and effectively for the treatment of elevated IOP in patients with open-angle glaucoma (13). Comparative studies in the UK, Canada, Israel, and the US have demonstrated efficacy of SLT is comparable to latanoprost the most commonly used first- line medical agent for the treatment of open-angle glaucoma. It is an in-office procedure that may effectively reduce IOP in most glaucoma patients. During SLT, a laser is used to target certain cells in the trabecular meshwork (TM), bringing about biological changes in the microstructure of the TM, resulting in an improved outflow of aqueous humor, thereby reducing IOP.

At Wills Eye Hospital Glaucoma Research Center, we compared outcomes of selective laser trabeculoplasty (SLT) with drug therapy for glaucoma patients in a multi-centered prospective randomized clinical trial (14). We enrolled sixty-nine patients (127 eyes) with open-angle

glaucoma or ocular hypertension who were randomized to SLT or medical therapy. Target intraocular pressure (IOP) was determined using the Collaborative Initial Glaucoma Treatment Study formula. Patients were treated with SLT (100 applications 360 degrees) or medical therapy (prostaglandin analog). Six visits over 1 year followed initial treatment. If target IOP range was not attained with SLT, additional SLT was the next step, or in the medical arm additional medications were added.

Sixty-nine patients were treated. Data collection terminated with 54 patients reaching 9 to 12-months follow-up. Twenty-nine patients were in the SLT group, 25 patients in the medical group. Baseline mean IOP for all eyes was 24.5 mm Hg in the SLT group, 24.7 mm Hg in the medical group. Mean IOP (both eyes) at last follow-up was 18.2 mm Hg (6.3 mm Hg reduction) in the SLT arm, 17.7 mm Hg (7.0 mm Hg reduction) in the medical arm. By last follow-up, 11% of eyes received additional SLT, 27% required additional medication. There was not a statistically significant difference between the SLT and medication groups. Therefore, IOP reduction was similar in both arms after 9 to 12-months follow-up. More treatment steps were necessary to maintain target IOP in the medication group, although there was not a statistically significant difference between groups. These results support the option of SLT as a safe and effective initial therapy in open-angle glaucoma or high risk ocular hypertension (14).

**A.2. Adherence:** Studies have shown that less than 50% of patients with glaucoma treated with prescription eye drops are indeed adherent to their medications (15-20). There are many obstacles to adherence with medical therapy for glaucoma: difficulty in placing eye drops, remembering to place eye drops, side effects, chronicity with no immediate tangible benefit, and cost. On the other hand, laser trabeculoplasty provides 100% adherence.

**A.3. Side Effects:** Medical therapy is frequently limited by ocular and systemic side effects. Local effects such as red eyes, allergic blepharoconjunctivitis, irreversible iris hyperchromia, periorbital fat atrophy, keratitis, and blurred vision may occur and not only affect quality of life, but impact ocular medication adherence. Even the preservatives in glaucoma bottles (most commonly benzalkonium chloride) are associated with problems such as exacerbation of dry eye symptoms. Of even deeper concern are systemic side effects of glaucoma medications, such as precipitating asthma, altering heart rate, lethargy, an increased risk of falling and subsequent injury, depression, rash which may lead to increased office visits, hospitalization, and rarely, death. In contrast, SLT may result in mild and transient IOP elevation, which is typically a minimal risk and rarely of any significance. Other side effects of laser are extremely rare including iritis, blurred vision, hyphema and keratitis.

**A.4. Cost:** Long-term use of eye drops can be costly, which may deter patients from adhering to their treatment regimens. Numerous cost analyses have been conducted to determine the most cost-effective treatment option for patients with newly diagnosed mild open-angle glaucoma (21-26). One observational study, conducted by Stein and coworkers, evaluated treatment of glaucoma with generic topical prostaglandin analogs (PGAs) versus treatment with laser trabeculoplasty (LTP). Using a Markov model with a 25-year horizon, the investigators compared the incremental cost-effectiveness of treating newly diagnosed mild open-angle glaucoma with PGAs, LTP, or observation only. Incremental cost-effectiveness of LTP over no treatment was \$16,824 per quality-adjusted life year. By comparison, incremental cost-effectiveness of PGAs versus no treatment is \$14,179 per quality-adjusted life year, and

PGAs provide greater health-related quality of life relative to LTP. The results supported that LTP can confer greater value since PGAs are 25% less effective due to poor patient adherence (21). A cost analysis by Cantor has shown that SLT is less expensive when compared with the cost of a topical generic glaucoma medication over a 5-year period. Patients treated with SLT initially, then followed by topical medication, had a cost saving of \$2.50 for every \$1.00 spent (25). Another observational study conducted by Seider found that SLT would be less costly than generic medication after 13.1 months (24). A 6-year cost comparison of SLT to primary medical therapy in Canada found that over a 3-year scenario, patients using SLT primary over “mono, bi and tri-drug therapy produced a 6-year cumulative cost savings of \$580.52, \$2042.82 and 2266.65 per patient” (26).

**A.5. Significance:** Cost-comparative studies in Canada, Australia, and the USA have tended to favor SLT as a first-line option. For these reasons, SLT would be an excellent alternative in the treatment of glaucoma, as it is reimbursed by Medicare and other insurance companies, has fewer side effects, and unlike the use of eye drops, requires no additional effort or adherence measures on the patient's part. Although glaucoma specialists consider the effect of SLT in lowering IOP to be similar to glaucoma medications, SLT is significantly underutilized as first-line treatment in glaucoma patients (24-26). Patient-related barriers may include lack of knowledge about SLT, confusion with other types of lasers, or fear of severe post-procedure complications. Ophthalmologists' attitudes may also be based on outdated information and inaccurate beliefs about SLT. Third party payers may not understand that SLT as first-line therapy may prove more convenient for patients, and may ultimately be more cost-effective (24-26).

**B. Study Aims:** The aims of this study are to:

**AIM 1:** Develop an Educational Intervention to directly inform patients with glaucoma of the benefit/risk of SLT versus ocular medications while also indirectly educating staff and physicians.

**AIM 2:** Conduct a randomized controlled trial to measure the effectiveness of an Educational Intervention with a group of patients by comparing conversions to SLT in the follow-up visits between the Usual Care group and the Educational Intervention group.

**AIM 3:** Assess the beliefs and attitudes of a group of ophthalmologists about SLT as first line therapy before and after viewing the Educational Intervention.

**Hypothesis:** *Better informed patients and ophthalmologists tend to select SLT in place of ocular medications as either first line or in place of medications after initially using medications.*

**C. Research Design and Methods:**

**C.1. Human Subjects and Informed Consent:** The study involves human subjects, all of whom will give informed consent prior to enrollment. The study will seek approval from Wills Eye Hospital's Institutional Review Board, and will be conducted in accordance with the Health Insurance Portability and Accountability Act. Study procedures will adhere to the Declaration of Helsinki for research involving human subjects.

**C.2. Development of the SLT Educational Intervention (AIM 1):** The Educational Intervention about SLT as first line therapy to treat glaucoma will be developed by the principal investigator, co-investigators, the research coordinator, and research assistants using the American Academy of Ophthalmology Practice Pattern Guidelines, and the Glaucoma Research Foundation resources. The intervention will be developed with the aim of improving patients' understanding of what laser treatment is, what are the benefits, and why it should be strongly considered as a first-line treatment for glaucoma before any medications. We will adapt the content from the Glaucoma Research Foundation web page as well as the material in the *Understanding and Living with Glaucoma* booklet ([www.glaucoma.org/treatment/laser-surgery.php](http://www.glaucoma.org/treatment/laser-surgery.php)).

Once the laser procedure is described alongside images and text written at the 4th grade reading level, a MS Powerpoint presentation will be developed, in consultation with a small group of patients (n=5) who have elected to have a laser procedure in at least one eye to treat glaucoma. We will share the Educational Intervention with these patients before and after they have the SLT procedure, and ask them to assist us in providing culturally and linguistically appropriate terms and language to describe the procedure.

We will also ask them to help us develop the "frequently asked questions" section including the answers that they feel would be most helpful to advocate for SLT as first line therapy for glaucoma. We will base these responses on the Glaucoma Research Foundation's web site intervention ([www.glaucoma.org/treatment/selective-laser-trabeculoplasty-10-commonly-asked-questions.php](http://www.glaucoma.org/treatment/selective-laser-trabeculoplasty-10-commonly-asked-questions.php)).

Once the SLT Educational Intervention is developed, we will produce a 10 minute video recording of glaucoma specialists, ([name] or [name]) explaining why patients would benefit from SLT as first line therapy to treat glaucoma. The video may include step-by-step footage of a patient being treated with laser at the Wills Eye Glaucoma Service and an interview with a patient after the procedure. This will provide patients with information about laser from a trusted source and a peer. The video will be embedded into the Powerpoint slide presentation.

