## **D.1 Data Management and Analysis**

**D.1.a. Assessment Measures:** The primary outcome measure is the number of patients who complete an SLT over the study period. Rates of SLT procedures will be compared between patients enrolled in the SLT Educational Intervention group versus the Usual Care group. Rates of SLT will be tracked in each group after patients are asked the first set of questions and after the Intervention group is shown the video. Follow-up eye exam appointments for patients in both groups will be tracked for a 6-month period to assess the number of patients who elect to have SLT.

The secondary outcome is to assess the beliefs and attitudes of patients and a group of ophthalmologists about SLT as first line therapy before and after viewing Educational Intervention. The research coordinator will ask all patients questions about their knowledge, beliefs, barriers, and attitudes about SLT vs. medication as first line treatment of glaucoma. These questions will be developed with [name], a psychologist and vision researcher at Sidney Kimmel Medical College with extensive experience in survey development and sampling techniques. She will be consulted during the development phase to revise and implement the following questions. If a more understandable explanation of the risks/benefits of SLT versus medications results in a significant increase in SLT treatments, that suggests that the real barrier is patient understanding and perhaps to a lesser extent physician education.

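### The intervention is specified as advocacy for SLT with booking help, and risk/benefit knowledge is not measured, so higher SLT uptake cannot show that patient understanding was the barrier

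*Combined protocol and SAP*

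**What the plan says.** **Purpose.** Aim 1 (section B) is to "directly inform patients with glaucoma of the benefit/risk of SLT versus ocular medications". The study hypothesis is that better informed patients and ophthalmologists tend to choose SLT.

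**Content.** C.2 is the only place that says what the material must contain. It is to improve patients' understanding of "what laser treatment is, what are the benefits, and why it should be strongly considered as a first-line treatment for glaucoma". The FAQ section is to hold the "answers that they feel would be most helpful to advocate for SLT as first line therapy for glaucoma", developed with five patients who have elected laser. The video shows glaucoma specialists "explaining why patients would benefit from SLT as first line therapy to treat glaucoma". C.2 also names a professional guideline and a foundation's web page and booklet as sources, and says that the FAQ responses will be based on that foundation's FAQ page.

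**Interpretation.** D.1.a makes completed SLT the primary outcome. Its interpretive sentence begins "If a more understandable explanation of the risks/benefits of SLT versus medications results in a significant increase in SLT treatments" and goes on to say that this would suggest patient understanding is the true obstacle, with physician education perhaps a smaller part.

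**Procedures.** Under C.4 both arms first see their ophthalmologist, who covers both options. The intervention arm then answers D.2.a, sees the presentation, answers D.2.b, may question the coordinator, and is helped to book SLT if the patient elects it. The usual-care arm may question the coordinator, answers D.2.a, and is given a telephone number without booking help.

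**The concern.** The protocol gives the intervention two descriptions. One is a two-sided explanation and the other is a case for SLT. The planned reading of the primary result depends on the first, but a team that builds the material from C.2 is instructed to produce the second.

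Uptake can rise because patients understand more, because a trusted specialist recommends SLT, or because booking is made easier. If the trial cannot tell these apart, a positive result would be published with an explanation it did not test. Later work might then go into patient education when the active ingredient was endorsement or scheduling.

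**Working it through.** No arithmetic lies behind the plan on this point. It gives no effect size, alpha or power, so there is no figure to reproduce. The check sets the sections side by side.

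**Step 1. Is the described intervention the specified one?**

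| Element | Aim 1 and D.1.a | C.2, including the video |
|---|---|---|
| Benefits of SLT | yes | yes |
| Risks of SLT | yes | not listed |
| Comparison with drops | yes, for both risks and benefits | only as a reason to consider laser before medication |
| Standard for FAQ answers | explanation | helpfulness in advocating SLT |

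The content left unrequired is available in the protocol. A.3 says that "SLT may result in mild and transient IOP elevation" and names iritis, blurred vision, hyphema and keratitis as extremely rare. That makes five laser side effects, listed beside the local and systemic effects of drops.

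A.1 gives efficacy figures for both sides:
- At 2 years, 44% of laser-first eyes (argon laser, not SLT) were controlled by laser alone, against 30% of medication-first eyes on timolol alone. The complements are 100 − 44 = 56% and 100 − 30 = 70%.
- In the centre's own SLT trial, 11% of eyes had additional SLT and 27% needed additional medication. Mean IOP fell by 24.5 − 18.2 = 6.3 mm Hg with SLT and by 24.7 − 17.7 = 7.0 mm Hg with medication. The protocol reports no statistically significant difference between groups.

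These figures show that balanced content could be drawn from the plan itself. They do not measure the size of the problem.

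**Step 2. Is understanding measured?**

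- D.2.a has six prompts: two on awareness that laser is an option or a first option, one on whether it was discussed that day, and three on willingness and reasons.
- D.2.b has five: questions about the programme, willingness (two), discussion of hesitation, and an offer to schedule.
- Prompts that test knowledge of a risk or benefit: 0 of 6 + 5 = 11.
- Timing: D.2.a precedes the presentation in the intervention arm, and D.2.b is asked in that arm only. No patient question is therefore asked in both arms after the exposure.
- Section F names Fisher's exact test for pre- against post-intervention survey answers. For patients, that comparison exists in one arm only.

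**Step 3. What does a between-arm difference in SLT contain?**

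The arms differ in at least three ways after the ophthalmologist visit:

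Difference in uptake = effect of information + effect of advocacy + effect of booking help

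The trial observes the left-hand side once and has no measurement that isolates any term on the right. A gain in understanding with no effect of persuasion or booking, and the reverse, could give the same uptake data. The earlier discussion with the ophthalmologist takes place in both arms, so it does not separate the terms either.

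**The case against.** The strongest case on the other side has five parts.

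- **The trial's purpose is open.** It is a 40-patient pilot whose title states the aim of increasing SLT adoption. A randomised comparison of uptake remains a valid estimate of what the package does. This stands: only the interpretation is at risk.
- **The D.1.a sentence is hedged.** It is conditional and says that a rise would suggest, not prove, the explanation. This stands, and it lowers the severity. Even a hedged inference needs some measurement that bears on it, and there is none.
- **The questions are not final.** D.1.a provides for a survey expert to revise them, and D.2.a already has awareness items and open prompts. Revision is a chance to make the repair, but nothing in the plan requires a knowledge item or a post-exposure question in both arms.
- **The sources may contain risk content.** C.2 is headed as implementing Aim 1 and draws on a guideline and foundation material. A reader might infer that the finished programme will contain no risks. The documents do not support that, because the sources cannot be seen. They show only that risk content is not required.
- **Patients hear about both options elsewhere.** A reader might also infer that patients will choose laser unaware of its risks. The documents do not support that either. The chart flag in C.3 asks the doctor for a detailed discussion of both options, C.4 places that discussion before the presentation, patients may question the coordinator or ask for a call from their doctor, and the consent pages are not in this copy.

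**Conclusion.** The point holds as one of internal consistency and interpretation. Aim 1 and D.1.a describe a risk/benefit explanation, while C.2 specifies benefits and advocacy. With no knowledge measure, no patient question asked in both arms after the exposure, and booking help in one arm only, a rise in SLT estimates the effect of the whole package on uptake. It cannot support the statement that understanding was the barrier.

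All 20 intervention patients receive the package, so the limitation applies to the entire primary comparison. It has no numerical size, because nothing in the plan allows uptake to be divided among information, persuasion and booking help.

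The conclusion rests on the text of B, C.2, C.4, D.1.a, D.2.a, D.2.b and F as written. It makes no assumption about what the source materials or consent form contain, and it is not a finding of patient harm. It should be fixed, preferably before the video is recorded, but it does not invalidate the trial.

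**What to change.** 1. **Reconcile C.2 with Aim 1.** Require the slides, FAQ and video script to state the A.3 risks of both laser and drops with the qualifiers given there. Require efficacy figures from A.1 with both sides shown: 44% with 30% (labelled as argon laser and timolol), 11% with 27%, and 6.3 with 7.0 mm Hg together with the lack of a significant difference. Replace the instruction to advocate for SLT with one for accurate, understandable answers about both options.
2. **Measure understanding.** Ask the same three or four scored risk/benefit knowledge items at the end of the visit in both arms, after the presentation in the intervention arm, and name the between-arm comparison in section F.
3. **Restate the D.1.a conclusion** as the effect of the package, including booking help, on SLT uptake. Claim a role for understanding only if the knowledge items differ between arms and booking help is the same in both.

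Balanced content alone would not rescue the inference while booking help differs between arms. If the sponsor keeps both the advocacy content and the one-sided booking help, step 3 is the minimum.

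The cost is a script and slide edit, a few survey items, a slightly longer visit and possibly a smaller uptake effect. With 20 patients per arm the knowledge comparison will be imprecise and should be reported with a confidence interval.

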### **C.3. Recruitment and Inclusion Criteria:**

**Patients:** A total of 40 patients will be recruited from the Wills Eye Hospital Glaucoma Care Specialists' private practice and the resident-run Glaucoma Clinic over an 6-month period for this pilot study. Eligible patients will be between 40 and 90 years of age, and have either high-risk ocular hypertension, primary open-angle glaucoma, or pseudo-exfoliation glaucoma with no previous laser trabeculoplasty. Eligible patients will be naive to medication and laser **or** currently being treated with glaucoma eye drop(s). Only patients within three years of a glaucoma-related diagnosis and stable intraocular pressure will be invited to participate.

After IRB approval, the patients' electronic medical records will be reviewed in advance of their next scheduled eye exam. Eligible patients will be invited to participate in the study by letter and/or telephone call, in advance of their scheduled appointment. Eligible patients may also be approached by our study team when checking in on the same day of their eye exam appointment.

All patients will be asked to provide written informed consent, prior to meeting with their ophthalmologist. Once patients are consented, a yellow-colored page with large font (**Patient Enrolled: SLT vs. Meds Study**) will be inserted into the patient's medical chart folder to alert the doctor that the patient is enrolled in the study and that both treatment options should be discussed in detail.

Those enrolled will be randomized to either the SLT Educational Intervention group (n=20) or the Usual Care group (n=20). The knowledge, beliefs, barriers, and attitudes about SLT vs. medication as first line treatment of glaucoma will be assessed in both groups.

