#### **C.4. Study Procedures:**

**Educational Intervention group:** The 20 patients randomized to the SLT Educational Intervention group will meet with their ophthalmologist who will discuss both SLT and medication options for treatment of glaucoma, which is currently standard of care. After their eye exam, the patient will meet with the research coordinator. The research coordinator will then ask the patient questions to assess their knowledge, beliefs, barriers, and attitudes about SLT vs. medication as first line treatment of glaucoma (See section D.2.a). The patient will then review the SLT Educational Intervention and be shown the PowerPoint presentation about SLT. After the presentation, the patient will be asked more questions (See section D.2 b). After viewing all information, the Intervention patient will have the opportunity to ask questions to the research coordinator about SLT. If the patient elects to schedule an SLT after the Educational Intervention, they will be assisted with making this appointment.

**Usual Care group procedures:** The 20 patients randomized to the Usual Care group will meet with their ophthalmologist who will recommend both SLT and medication options for treatment of glaucoma, which is currently standard of care. After their eye exam, the patient will meet with the research coordinator who will answer any questions they have about treatment options. The research coordinator will then ask the patient questions to assess their knowledge, beliefs, barriers, and attitudes about SLT vs. medication as first line treatment of glaucoma (See section D.2.a). The Usual Care group will not be exposed to SLT Educational Intervention and will not be asked to watch a video about SLT. If the patient elects to have SLT at any point during the study, we will provide the phone number for them to schedule the procedure. Patients in the Usual Care group will not be assisted with making any SLT appointments.

If patients in either group would like to consult with their ophthalmologist again, we will provide a message to the physician and he/she will call the patient to discuss treatment options again. Doctors will be masked to the group assignment to reduce biasing the outcome. We will track how many patients wanted to speak to their ophthalmologist over the phone or in person in both groups and the outcome of these calls.

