**D.2.a. Questions for Patients in Both Groups after Consenting and Eye Exam**

Are you aware that glaucoma can be treated with laser therapy instead of eye drops?  
Did you know that laser therapy is a possible first option for treating glaucoma before eye drops?  
Did you discuss laser therapy with your glaucoma doctor today?  
Would you consider having laser treatment? Why or why not?  
Would you consider having this laser therapy instead of filling your prescription for eye drops?  
If no, please describe reasons.

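### The comparator is prompted, surveyed usual care, so the trial measures what the intervention package adds to that and not its effect over routine care; two survey items also inform the patients they question.

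*Combined protocol and SAP*

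**What the plan says.** Aim 2 (section B) sets up the trial as a comparison of conversions to SLT "between the Usual Care group and the Educational Intervention group". Section C.3 plans 40 patients, 20 per arm, and states: "All patients will be asked to provide written informed consent, prior to meeting with their ophthalmologist". After consent, a large-font yellow page goes into the chart "to alert the doctor that the patient is enrolled in the study and that both treatment options should be discussed in detail". Neither arm is exempt.

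In C.4, Usual Care patients see an ophthalmologist "who will recommend both SLT and medication options for treatment of glaucoma, which is currently standard of care". They then meet the research coordinator, who answers their treatment questions and administers the D.2.a survey. Intervention patients also answer D.2.a, before they see the presentation. The first D.2.a item asks whether the patient is aware that laser can take the place of drops. The second reads "Did you know that laser therapy is a possible first option for treating glaucoma before eye drops".

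Section A.5 says that "SLT is significantly underutilized as first-line treatment in glaucoma patients" and suggests patients' lack of knowledge and ophthalmologists' outdated views as possible reasons. Section D.1.a would read a significant rise in SLT as a sign that patient understanding is the real barrier, with physician education perhaps mattering less.

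**The concern.** The control arm carries the label Usual Care, yet it receives study procedures aimed at the two barriers that A.5 suspects. The chart page acts on what the doctor does, and the first two survey items act on what the patient knows. Both come at the enrolment visit, ahead of most of the six months over which SLT is counted.

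Three conclusions are at stake:

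- **The Aim 2 result.** A reader will take a difference from Usual Care as the gain over ordinary practice. A small difference could be read as a failure of education, although controls also received some of the key information.
- **The barrier inference in D.1.a.** Doctors are prompted in both arms, so the contrast cannot say how much physician behaviour contributes.
- **The survey answers.** An item that states the fact it asks about invites agreement. It also comes before the D.2.a questions on willingness to have laser, which D.2.b largely repeats after the video. The pre/post comparison in section F may therefore start from an already informed baseline.

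**Working it through.** The plan has no figure to reproduce for this point: it gives no expected SLT rate, effect size, significance level or power. The check is a comparison of the arms.

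**1. What each arm receives (C.3, C.4, D.2.a, D.2.b)**

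| Step | Intervention | Usual Care |
|---|---|---|
| Consent before seeing the doctor | yes | yes |
| Chart page | yes | yes |
| Doctor covers both options | described as *discuss* | described as *recommend* |
| D.2.a survey | yes | yes |
| Coordinator answers questions | yes, after the presentation | yes, before the survey |
| Presentation and video | yes | no |
| D.2.b questions | yes | no |
| Scheduling SLT | assisted | phone number only |

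The arms are meant to differ in the presentation and video, D.2.b and booking help. The chart page and D.2.a are common to both.

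**2. What the contrast estimates**

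Let p(s,k) be the proportion completing SLT, with s = 1 if the shared study procedures are present and k = 1 if the package is given.

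- The trial estimates p(1,1) − p(1,0).
- The effect of the package over routine care is p(0,1) − p(0,0).
- The effect of all study procedures together over routine care is p(1,1) − p(0,0).

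Both p(0,0) and p(0,1) are unobserved, since no arm or outside cohort goes without the page and survey. The trial's contrast differs from the package effect over routine care by

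D = [p(1,1) − p(1,0)] − [p(0,1) − p(0,0)].

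D is zero if the package adds the same number of percentage points with or without the shared procedures. D is negative (dilution) if the survey has already told controls part of what the video would. D is positive if a prompted discussion makes patients more receptive to the video. Nothing in the documents fixes its sign or size.

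**3. Why the control rate still matters in a small trial**

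With 20 per arm, one patient is 1/20 = 5 percentage points. Assume a two-sided Fisher exact test at 0.05; section F names Fisher's test only for survey answers, and the level is an assumption. Against 0 of 20 controls, significance needs 5 of 20 in the Intervention arm. Against 2 of 20 it needs 9. If shared procedures added two conversions to each arm, 5 versus 0 would become 7 versus 2. The difference is 5/20 = 25 points in both cases, but 7 falls short of 9. This is arithmetic on the test and does not estimate what the page or survey does.

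**4. The wording in C.4**

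C.4 has doctors *discuss* both options in one arm and *recommend* both in the other, and also says that doctors are masked to assignment. Masked doctors cannot act differently by arm, so the two descriptions cannot both be meant literally.

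**The case against.** The strongest reply is that procedures shared by both arms do not bias a randomised comparison. That is correct. A reader might infer that the trial is biased, or that its effect cannot be estimated at all. The documents support neither reading: the contrast is valid for the package added to prompted care.

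A second reply is that C.4 calls presentation of both options standard of care, so the page may change little. This stands in part. Underuse of SLT in A.5 concerns uptake and does not show that discussion is rare; A.5 offers its barriers only as possibilities. But no data on routine discussion in these clinics are given either.

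Third, the only page text shown in C.3 is an enrolment notice naming the study. The detailed discussion is the page's stated purpose and may not be printed on it. Cutting the page to an enrolment statement might therefore change nothing, and patients will in any case have consented to an SLT study before seeing the doctor. The prompt also keeps discussion uniform. A demand that it be removed does not follow.

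Fourth, D.1.a says that the questions will be revised with a survey specialist, and they are asked after the doctor has covered both options. How much the two items add is unproven. Their wording still informs as drafted, and the planned revision is the natural time to change it.

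**Conclusion.** The point holds as one about what is estimated and how the survey is worded. The trial can estimate the effect of presentation and video, D.2.b questions and booking help, added to prompted and surveyed usual care. It cannot estimate the effect over routine care outside the study, and it cannot separate patient understanding from physician behaviour as D.1.a proposes. Booking help in one arm only further limits any attribution to understanding.

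A reader might go on to infer that the control rate is inflated and the benefit understated by some number of points. The documents do not support that. They give no SLT rates, the same procedures act in the Intervention arm, and D could be zero or of either sign. No magnitude should be attached.

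The conclusion assumes that the page and D.2.a are applied in both arms as written. If neither changes behaviour, the estimate is unaffected and only the label and the leading items remain at issue. For a 40-patient pilot this is an inexpensive improvement and not a failure of the design.

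**What to change.** 1. **Survey.** Reword the first two D.2.a items so that they do not inform, for example *Which treatments for glaucoma do you know of?* and *Which can be used as the first treatment?* Cost: open answers need a simple coding scheme.
2. **Comparator and conclusions.** In Aim 2, C.4 and D.1.a, describe the comparator as prompted or enhanced usual care, and limit the conclusion to the package added to it. Qualify the D.1.a inference about the real barrier: doctors are prompted in both arms, and booking help is part of the package. Cost: text only, and a narrower claim.
3. **Doctor discussion.** Reconcile *discuss* and *recommend* in C.4 so that one description applies to both arms, consistent with masking. Cost: one sentence.

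Dropping the chart prompt is optional. It might bring the comparator closer to routine care, at the price of less uniform discussion in both arms. None of the three changes affects sample size or follow-up.
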